7.6 Follow-up of subjects withdrawn from treatment

Patients who withdraw from the treatment will be followed-up. Because the patients are asked to enter the number of motor imagery sessions each day in a diary, it still provides information concerning the effectiveness of motor imagery training.

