5. TREATMENT OF SUBJECTS

5.1 Investigational product/treatment

The treatment that the experimental group receives is motor imagery training, in addition to the regular treatment. The control group receives regular treatment only. Motor imagery is the mental state in which an individual performs an activity mentally and explicitly feels himself performing it, without actually performing the activity physically (47). This mentally rehearsing of a task can be done with two different strategies, by visual or kinetic motor imagery. When a person imagines the movement from a third person perspective, it is called visual motor imagery. When a person imagines the movement from a first person perspective, as if they are performing the movement themselves, it is called kinetic motor imagery (63). Research has shown that the neural structures activated during kinetic motor imagery are more similar to the neural structures activated during movement execution, than when visual motor imagery is performed (64,65). For that reason, the imagery training of DRF-patients in the present study will consist of kinetic imagery.

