Three weeks later, which is 4 weeks after injury, the patients return to the hospital to remove the cast. At that moment, the first measurements will be performed. All tests will be performed by the study coordinator. Directly after cast removal, when they are still at the hospital, dexterity, the level of pain and pain relief, grip strength and range of motion will be determined. The PRWHE will be performed one day later by phone. Two weeks after cast removal, the second measurements will be conducted. Function, dexterity, the level of pain and pain relief, grip strength and range of motion will be measured.

The measurements will take place in the University Medical Center Groningen. The PRWHE and the VAS can be scored by the patients themselves, while the measurements with the SODA, goniometer and dynamometer will be conducted by the study coordinator. It is expected that the first measurements will take 30 minutes to complete, and the second measurements 35 minutes.

As explained in chapter 7.1, function is measured using the PRWHE. The PRWHE is a self-reporting instrument that determines the level of disability during specific and usual activities, and also contains some items to determine the level of pain and aesthetics (59). It takes on average 4 minutes to complete the questionnaire (61).

A digital goniometer is used to determine the active ROM. It is expected that the process of measuring ROM takes 6 minutes to complete.

Grip strength is measured using a hydraulic dynamometer (73). The strength of four different grips will be determined, according to the protocol as described by Mathiowetz et al. (1984). It is expected that the procedure to measure the grip strengths takes 4 minutes to measure both sides.

Dexterity is determined using the SODA. The SODA is a performance-based test, which measures the level of disability during activities of daily living (68). We expect that it takes 20 minutes to complete it. Instructions of the SODA will be given according to the protocol described by Van Lankveld et al. (1996).

The level of pain and the level of pain relief are determined using a VAS (75), a self-reporting scale. It is expected that it only will take a few seconds to complete it.

7.4 *Withdrawal of individual subjects*

The patients are free to withdraw from the study at any time, for any reason, and without consequences. Patients are withdrawn when the study coordinator thinks that participation by a

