patient is unsafe, or when the medical condition changes in such way that participation is impossible or unadvised.

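### Sections 7.4 to 7.6 do not separate stopping the training from leaving the study, so outcomes of patients with a bad course can be lost, and the loss can differ by arm

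*Combined protocol and SAP*

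**What the plan says.** Section 7.4 gives two ways out of the study. The first is the patient's own choice: "The patients are free to withdraw from the study at any time, for any reason, and without consequences". The second is a decision made for her. The text reads "Patients are withdrawn when the study coordinator thinks that participation by a" patient would be unsafe, or "when the medical condition changes in such way that participation is impossible or unadvised". Neither route names an arm. Section 7.4.1, the place for specific criteria, is marked not applicable.

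Section 7.5 replaces a withdrawn patient with the next eligible one, who is put in the same group.

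Section 7.6 is the only rule on follow-up after a patient stops: "Patients who withdraw from the treatment will be followed-up". It does not say which outcomes are collected or when. Its stated reason is the training record: "Because the patients are asked to enter the number of motor imagery sessions each day in a diary".

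Section 5.1 fixes what treatment means in each arm: "The treatment that the experimental group receives is motor imagery training, in addition to the regular treatment", and "The control group receives regular treatment only".

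Four other places matter:
- Section 7.2 says that neither patients nor the researcher are blinded, and 7.3 has the study coordinator perform all tests.
- Section 9.3 promises intention to treat for both groups. Section 9 gives no method for missing outcomes.
- Section 5.2 leaves out of the analysis any patient who reports other interventions or treatments during the study.
- Section 7.3 says of the primary outcome at T1: "The PRWHE will be performed one day later by phone".

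**The concern.** Patients withdrawn because their medical condition has changed are likely to be those recovering poorly. Section 4.3 itself links complications to a worse functional result. Under 7.4 and 7.5 such a patient leaves and another takes her place. This restores the group count but not her outcome, so the analysed group looks healthier than the group that was allocated.

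The handling may also be unequal. In the training arm, a medical setback can be recorded as stopping the training, and 7.6 then keeps the patient in follow-up. A control has no training to stop and no imagery sessions to enter in a diary, so if anything is recorded for her as a withdrawal, it is a withdrawal from the study. The person who chooses between these labels knows the arm and has no written criteria. At stake is a biased comparison on the primary outcome, and an analysis set that does not match the one promised in 9.3.

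**Working it through.** **1. The rules side by side**

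| Situation | Training arm | Control arm |
|---|---|---|
| Not withdrawn | T1 and T2 at routine visits | T1 and T2 at routine visits |
| Stops study treatment only | 7.6: followed up | Cannot arise (5.1) |
| Withdrawn from the study under 7.4 | No outcome collection stated; replaced (7.5) | No outcome collection stated; replaced (7.5) |

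The third row is a gap in both arms. The second row is where the arms can diverge, because it offers one arm a label that keeps the patient in follow-up.

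**2. The plan's own figures**

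Section 4.4 gives a target difference of about 5 PRWHE points (5.3 from the recovery model), an SD of 26.13, and N = 52, which is 26 per arm with equal groups. The stated N reproduces. For the within-between interaction with f = 0.20, m = 2 measurements and an assumed default correlation of 0.5:

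lambda = f² × N × m / (1 − rho) = 0.04 × 52 × 2 / 0.5 = 8.32, with 1 and 50 degrees of freedom, giving power 0.807.

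This takes the plan's effect-size setting at face value.

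**3. Effect on the mean difference**

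The PRWHE is scored so that higher is worse. Let a fraction p of an arm be lost, with lost patients scoring d points worse than those retained. The full-arm mean is (1 − p) × m + p × (m + d) = m + p × d, where m is the retained mean. The retained mean therefore looks better by p × d. Replacement by patients like those retained does not change this. For the benefit of training (control minus training):

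observed benefit = true benefit − p(control) × d(control) + p(training) × d(training)

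The documents give neither p nor d. Assuming p of 5-15% and d of 20-30 points in controls, and no loss in the training arm:

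| p | d = 20 | d = 30 |
|---|---|---|
| 0.05 | 1.0 | 1.5 |
| 0.10 | 2.0 | 3.0 |
| 0.15 | 3.0 | 4.5 |

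The shift is 1.0 to 4.5 points against training.

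A second range takes d from the plan's own numbers, from 5.3 (one week of recovery) to 26.13 (one SD):
- 1 of 26 controls lost (3.8%): 0.2 to 1.0 points
- 2 of 26 lost (7.7%): 0.4 to 2.0 points
- 4 of 26 lost (15.4%): 0.8 to 4.0 points

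If the loss falls in the training arm instead, the same amounts favour training. If p and d are equal in both arms, the terms cancel.

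**4. Effect on the interaction**

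The sample size rests on the group-by-time interaction. That contrast shifts by p × (d at T2 − d at T1), which is zero if the lost patients are equally worse at both times.

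**5. Effect on power**

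Without replacement, losing 1 to 6 controls and no training patients lowers power from 0.807 to between 0.800 and 0.749. Replacement would restore the count. Power is therefore the smaller issue, and selection the larger.

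**The case against.** A reader might infer that controls alone are left without follow-up, that a control with a setback can only be taken out of the study, and that loss must therefore differ by arm. The documents do not support this.
- Section 7.4 ends participation in both arms. A training patient withdrawn under it has no stated outcome collection either, unless 7.6 is stretched to cover her.
- A control who has a setback but is not withdrawn stays in scheduled follow-up at routine visits. For her, participation is two sets of measurements, and section 10.4 calls the risk of taking part negligible, so the trigger in 7.4 may rarely be met.
- No loss rate is given, overall or by arm.

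The size can also be challenged. The event rates and score deficits are assumed, total loss in one arm with none in the other is an extreme, and a constant deficit would leave the interaction untouched. Section 5.2 narrows the contrast further: where a setback leads to another treatment, it removes the patient's results in either arm.

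All of this stands. It limits the point to a risk of unknown size and direction. It does not supply the missing rule. Nothing in 7.4 to 7.6 secures an outcome after study withdrawal, and an intention-to-treat analysis cannot use outcomes that were never collected. The 5.2 exclusion is a further departure from 9.3 and does not answer the point. The diary is a fair reason to keep following patients who trained only in part, but it should not be the only reason.

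**Conclusion.** The point holds as a gap in the plan. Sections 7.4 to 7.6 do not distinguish stopping the training from leaving the study. They state no outcome collection after study withdrawal in either arm, and they replace the patient. The one follow-up rule fits only the training arm in practice. This conflicts with intention to treat for both groups in 9.3. It allows, but does not force, loss that differs by arm, since an unblinded coordinator decides without criteria.

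The 1.0 to 4.5 points are a worst-case illustration for a mean difference at one time point. They rest on an assumed 5-15% loss in one arm only and an assumed deficit of 20-30 points. Against a target of about 5 points that would matter. With one or two patients lost and a smaller deficit, the shift is a fraction of a point. The direction cannot be known in advance. The change is worth making because it is cheap and protects the primary outcome.

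**What to change.** Reword 7.4 to 7.6 so that outcome collection does not depend on what is decided clinically about training or participation:
- Seek the PRWHE at T1 and T2 for every included patient in both arms, unless she withdraws consent to be measured. Use the phone where she cannot attend, as 7.3 already does at T1.
- Record other tests that cannot be done as not done, with the reason.
- Report withdrawals and their reasons by arm.
- Keep withdrawn patients in the analysis in their allocated group, even if they are replaced under 7.5.
- Reconcile the exclusion in 5.2 with 9.3. Otherwise outcomes collected under the new wording could still be left out of the analysis.

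The cost is a short amendment and a few calls. The questionnaire takes about 4 minutes, and both arms are already phoned weekly under 7.3. The downside is that some PRWHE values will come by phone rather than on site, so the mode should be recorded for each value.

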7.7 Premature termination of the study

When interim-analysis indicates that motor imagery causes deterioration of the hand function, causes severe pain, or causes other unwanted effects, this study will be terminated.

8. SAFETY REPORTING

8.1 Section 10 WMO event

In accordance to section 10, subsection 1, of the WMO, the investigator will inform the subjects and the reviewing accredited METC if anything occurs, on the basis of which it appears that the disadvantages of participation may be significantly greater than was foreseen in the research proposal. The study will be suspended pending further review by the accredited METC, except insofar as suspension would jeopardise the subjects' health. The investigator will take care that all subjects are kept informed.

8.2 Adverse and serious adverse events

Adverse events are defined as any undesirable experience occurring to a subject during the study, whether or not considered related to [the investigational product / the experimental treatment]. All adverse events reported spontaneously by the subject or observed by the investigator or his staff will be recorded.

A serious adverse event is any untoward medical occurrence or effect that at any dose:

- results in death;
- is life threatening (at the time of the event);
- requires hospitalisation or prolongation of existing inpatients' hospitalisation;
- results in persistent or significant disability or incapacity;
- is a congenital anomaly or birth defect;
- is a new event of the trial likely to affect the safety of the subjects, such as an unexpected outcome of an adverse reaction, lack of efficacy of an IMP used for the treatment of a life threatening disease, major safety finding from a newly completed animal study, etc.

All SAEs will be reported through the web portal *ToetsingOnline* to the accredited METC that approved the protocol, within 15 days after the sponsor has first knowledge of the serious adverse reactions..

SAEs that result in death or are life threatening should be reported expedited. The expedited reporting will occur not later than 7 days after the responsible investigator has first knowledge of the adverse reaction. This is for a preliminary report with another 8 days for completion of the report.

8.2.1 *Suspected unexpected serious adverse reactions (SUSAR)*

Not applicable.

8.2.2 *Annual safety report*

Not applicable.

8.3 *Follow-up of adverse events*

All adverse events will be followed until they have abated, or until a stable situation has been reached. Depending on the event, follow up may require additional tests or medical procedures as indicated, and/or referral to the general physician or a medical specialist.

9. STATISTICAL ANALYSIS

9.1 *Descriptive statistics*

Patient characteristics are presented using descriptive statistics for the potential confounding variables.

Data of the main outcome measure are of interval level of measurement. The ROM and grip strength are of ratio level of measurement. Hence, the descriptive statistics of these outcome measures are presented by the mean and standard deviation. Dexterity is measured using the SODA, and the data of this instrument are of ordinal level of measurement. Therefore, the descriptive statistics are presented by the median and range. Pain is measured using the VAS, which provides data of interval level of measurement. So, the descriptive statistics are presented by the mean and standard deviation.

9.2 *Univariate analysis*

The effectiveness of motor imagery training will be determined with use of a multivariate analysis for the parametric data (as described later in chapter 9.3). The non-parametric data are analyzed using a Mann-Whitney U test for each variable, to determine whether the groups are different. This test is also used when the data is not normally distributed.

9.3 *Multivariate analysis*

With use of a MANOVA, the difference between the experimental and control group will be determined for each measurement time and for each variable. There are two factors included in the analysis; a between factor 'group' and a within factor 'time'. The hypothesis is tested using two-tailed tests, with a significance level of 5%. The data of the patients in both groups will be analyzed using an intention to treat analysis.

9.4 *Interim analysis (if applicable)*

An interim analysis will be conducted to determine the effect of motor imagery training on hand function, dexterity, ROM, grip strength and pain. When the results of this analysis shows serious unwanted effects of motor imagery training, this study will be terminated.

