4.4 Sample size

This is the first study that investigates the functional outcome effect of motor imagery training during the immobilization period in DRF-patients. Therefore, the sample size calculation cannot be based on data of an imagery intervention during immobilization on function after a DRF. In this study, function is the primary outcome variable, and it is measured using the Patient Rated Wrist/Hand Evaluation (PRWHE). This instrument is derived from the Patient Rated Wrist Evaluation (PRWE). The only difference between the PRWE and PRWHE is that the PRWHE contains extra questions about aesthetics. It still contains the originally validated questions,

format and scoring system. The added questions about aesthetics are not part of the scoring. Therefore, it can be treated as the PRWE (59). The PRWE is proven to be the most responsive instrument to measure outcome in DRF-patients (60), as it measures disability during usual and specific activities and also documents pain. Subjects can score from 0 to 100 on the PRWHE; 0 indicates no problems at all and 100 indicates large functional difficulties and severe pain. The sample size calculation will be based on the expected outcomes of motor imagery training on the PRWHE.

Description of calculation process

A previous study has described the change of the PRWE-score over time as a result of the process of natural recovery after a DRF (61). Based on the results of this study, a mathematical model was created using Matlab R2010a that estimates the PRWHE-scores between data collection moments. This way, a model was build to estimate the natural recovery process with respect to the outcome of the PRWHE. Using this model, it could be determined what the decrease of the PRWHE-score is, two weeks after cast removal. The results of this model showed that a decrease of 10 points can be expected between the first (T1) and second measurements (T2). This decrease is due to natural recovery, and therefore, we expect it to be present in both groups.

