Based on expert's knowledge, we find a 1 week lead in the functional recovery of the motor experimental group on the control group a clinically significant difference. With use of the mathematical model, the change in the PRWHE-score after 1 week after cast removal could be estimated. Next, the mean standard deviation of the PRWHE-scores over time was calculated. By dividing the change in the PRWHE-score by the mean standard deviation, the effect size was calculated. Now, the sample size could be calculated using the statistical power analysis software G*Power 3 (62).

Effect size calculation

The model describing the change in the PRWHE-score as result of natural recovery following a DRF, showed that 1 week after cast removal a decrease of 5.3 points on the PRWHE can be expected, which indicates improved function. This would mean that the experimental group would show an extra decrease of 5 points on the PRWHE, two weeks after cast removal.

The mean standard deviation was calculated using the following formula:

$$\sigma = \sqrt{\frac{n_x^2 s_x^2 + n_y^2 s_y^2 - n_y s_x^2 - n_x s_y^2 - n_x s_x^2 - n_x s_y^2 + n_y n_x s_x^2 + n_y n_x s_y^2 + n_x n_y (\bar{X} - \bar{Y})^2}{(n_x + n_y - 1)(n_x + n_y)}}$$

This provided a mean standard deviation of 26.13... points.

The effect size was calculated using the following formula:

$$ES = \frac{\mu_1 - \mu_2}{\sigma}$$

This provided an effect size of 0.20...

Settings for sample size calculation

Test Family: F-tests

Statistical test: Repeated Measures ANOVA, within-between interaction

Effect size: 0.20

Significance level $\alpha = 5\%$

Preferred power = 80%

Number of groups: 2

Number of measurements: 2

Other settings were kept as the default setting.

Sample size calculation

The effect size, preferred power, significance level and two-tailed testing were entered in

G*Power 3. Running the program resulted in a calculated sample size of 52 patients.

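### The 52 patients and 80% power belong to a group × time ANOVA of PRWHE alone, but the analysis section decides effectiveness by a MANOVA of all parametric outcomes and names no primary PRWHE contrast

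*Combined protocol and SAP*

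**What the plan says.** Section 4.4 (Sample size) states that "function is the primary outcome variable, and it is measured using the Patient Rated Wrist/Hand Evaluation (PRWHE", and ties the calculation to that outcome: "The sample size calculation will be based on the expected outcomes of motor imagery training on the PRWHE". The settings are "Statistical test: Repeated Measures ANOVA, within-between interaction" and "Effect size: 0.20", with two groups, two measurements, 5% significance, 80% power and the program's other defaults. The result is 52 patients.

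Section 9 describes a different analysis. Section 9.2 says "The effectiveness of motor imagery training will be determined with use of a multivariate analysis for the parametric data". Section 9.3 continues: "With use of a MANOVA, the difference between the experimental and control group will be determined for each measurement time and for each variable". The factors are group (between) and time (within), tested two-tailed at 5%. Section 9.1 classes PRWHE, range of motion, grip strength and VAS pain as interval or ratio data, so all four fall under the MANOVA. Dexterity (SODA) is ordinal and goes to a Mann-Whitney U test, as do any data that are not normally distributed.

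Section 9 does not say:
- which PRWHE comparison is primary (first visit, second visit or group × time);
- whether the joint test must be significant before single variables are read;
- how the tests for each variable and visit share the 5% level.

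**The concern.** The power statement and the analysis should refer to the same test. Here the calculation concerns one degree of freedom on one outcome, while the analysis section lets a multivariate procedure decide effectiveness and treats PRWHE like any other parametric variable.

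Two things are at stake. First, nobody can say what power the trial has for its decisive test, because that test is not identified. Second, several results could later be presented as the answer: the joint test, PRWHE at either visit, or the PRWHE interaction. Section 7.2 says that neither patients nor the researcher are blinded, so a choice left open until the data are in is exposed to knowledge of the results. A significant joint test could also come from one pinch grip or one direction of wrist movement and be reported as a benefit on function.

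**Working it through.** **Inputs.** From 4.4: f = 0.20, m = 2 measurements, 2 groups, α = 0.05, N = 52. The correlation between visits is not printed. I assume the program defaults, ρ = 0.5 and no sphericity correction; 4.4 says the remaining settings were left at default.

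**Step 1: reproduce the plan's figure.** For the within-between interaction, λ = N·m·f²/(1 − ρ) = 52 × 2 × 0.04 / 0.5 = 8.32, on F(1, 50). Power is 80.7%. N = 50 gives λ = 8.00 and 79.1%, so 52 is the smallest even total that reaches 80%. The figure reproduces for PRWHE alone.

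**Step 2: joint test of the same interaction.** With p outcomes, the two-group joint test on change scores (Hotelling T²) is referred to F(p, N − p − 1). Let every pair of outcomes have correlation r. The PRWHE noncentrality of 8.32 is then multiplied by
- (1 + (p − 2)r) / [(1 − r)(1 + (p − 1)r)] if only PRWHE responds;
- p / (1 + (p − 1)r) if all outcomes respond by the same standardised amount.

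I use two counts. p = 4 takes PRWHE, range of motion, grip and pain as one variable each. p = 13 takes PRWHE, six directions of motion, four grips and two VAS scales (1 + 6 + 4 + 2), injured hand only. The plan fixes neither count.

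| p | Pattern | r = 0 | r = 0.3 | r = 0.5 | r = 0.7 |
|---|---|---|---|---|---|
| 4, F(4, 47) | only PRWHE | 58% | 67% | 80% | 96% |
| 4, F(4, 47) | all equal | >99% | 91% | 80% | 70% |
| 13, F(13, 38) | only PRWHE | 31% | 42% | 58% | 85% |
| 13, F(13, 38) | all equal | >99% | 80% | 58% | 43% |

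Two checks on the multipliers. At p = 13, r = 0, only PRWHE: multiplier 1, λ = 8.32, 31%. At p = 13, r = 0.5, only PRWHE: (1 + 5.5) / (0.5 × 7) = 1.857, λ = 15.45, 58%.

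**Step 3: the joint test as a gate.** A PRWHE claim would then need both the joint test and the PRWHE test to be significant. The probability of both cannot exceed that of the second alone, which is 80.7% for the interaction. Simulation with only PRWHE responding gives about 29%, 38%, 52% and 72% for p = 13 at r = 0, 0.3, 0.5 and 0.7, and about 56%, 63%, 72% and 79% for p = 4.

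**Step 4: a PRWHE comparison at one visit.** Section 9.3 also reads differences by visit. With the same f = 0.20, λ = N·f² = 52 × 0.04 = 2.08 on F(1, 50), and power is about 29% before any gain from covariates. The 80% does not carry over to this comparison either.

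**The case against.** The strongest reply is that section 9.3 does plan a PRWHE comparison, since PRWHE is one of the variables for which the group difference is determined. With two visits, the univariate PRWHE group × time test from such a model is the same F test that 4.4 sized. On that reading test and sample size agree, and section 9 mentions no gate. This stands. A reader might infer that the planned analysis cannot answer whether function improved; the documents do not support that. What remains is that section 9 never says that this is the test that decides.

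A reader might also infer that the joint test usually has lower power. The table does not support that as a general statement. Power exceeds 80.7% in several cells, and the hypothesis in 1.3 is that all outcomes improve, which is the favourable pattern when correlations are low. Only a different, and possibly much lower, power can be claimed.

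Finally, 13 variables is an inference from 7.1.2. Section 7.1 speaks of five outcome measures, four of them parametric, and motion and grip are measured on both hands, so other counts are possible. Data judged non-normal would leave the MANOVA altogether. These objections limit the size of the effect but do not supply the missing primary contrast.

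**Conclusion.** The point holds as a mismatch and an omission. The calculation covers the PRWHE group × time interaction (80.7% at N = 52). The analysis section names a MANOVA read by visit and by variable, identifies no primary PRWHE contrast and leaves the role of the joint test open. The stated 80% therefore cannot be attached to the analysis as written.

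Joint-test power at the plan's settings runs from 31% to above 99% across the scenarios shown. That range rests on assumed outcome counts, a common correlation between outcomes, the response pattern, and ρ = 0.5 between visits. Two statements need none of the outcome assumptions: a significant joint test does not by itself establish a benefit on function, and gating cannot raise the power of the PRWHE test.

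All figures take f = 0.20 as entered. Section 4.4 obtains 0.20 as a difference divided by a standard deviation (5.3 / 26.13 = 0.203). Whether that quantity may be entered as f is a separate question, so agreement between test and calculation does not by itself secure 80% power.

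Severity: should-fix. Clear wording resolves it if the interaction is kept as the primary test.

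**What to change.** In 9.2 and 9.3, name one PRWHE test as the sole confirmatory test at two-sided 5%. State that it does not depend on the result of any MANOVA, and report it as a mean difference with a 95% confidence interval. The group × time test already in 4.4 is the choice that matches N = 52; its estimate is the between-group difference in mean PRWHE change from the first to the second measurement.

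Describe any MANOVA, and all other tests by variable and by visit, as supportive.

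If another PRWHE contrast is preferred, such as the group difference at the second visit, restate the power in 4.4 for that contrast. Asking only for a linear model of PRWHE, without visit or contrast, would leave the same gap.

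Cost: wording in 9.2 and 9.3 and no new data if the interaction is kept; a new power calculation in 4.4, and possibly a different sample size, if it is not. The joint test is lost as a headline result.
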